## 6.7 Study Duration

Individual subject participation is expected to last up to one year following alloHSCT, including a 6-week treatment period and a 42-week follow-up period. In addition, there is a screening period lasting approximately 2 weeks.

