8. KPS  $\geq$  60
9. Is a candidate for anti-graft-vs-host-disease (GvHD) prophylaxis that includes:
  - a. A calcineurin inhibitor (either tacrolimus [FK 506] or cyclosporine A), in combination with either methotrexate (MTX), mycophenolate mofetil (MMF)
10. Ability to understand and willingness to sign a written informed consent form

Inclusion criteria pertaining specifically for subjects scheduled to receive RGI-2001:

11. If female of childbearing potential, must have had a negative serum pregnancy test prior to enrollment and must have agreed to use a double barrier method of contraception for 90 days following the last dose of RGI-2001
12. If male, must be sterile or willing to use an approved method of contraception from the time of informed consent to 90 days after the last dose of RGI-2001

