## 10.7 Pregnancy

Although pregnancy is not considered an AE or SAE, all pregnancies occurring in subjects enrolled in this study or in a female partner of a male subject in this study must be reported to the Sponsor within 24 hours of becoming aware, and followed to outcome, even after the end of the study. If a female subject inadvertently becomes pregnant while on study treatment, the subject will immediately be removed from the study. Any pregnancies that occur within 150 days for females or 90 days for males following the last dose of study treatment must be reported to the Sponsor.

Refer to [Appendix 6](#) for complete information regarding pregnancies including highly effective contraceptive methods and recording and reporting guidelines in the event of a pregnancy.

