## APPENDIX 6 CONTRACEPTIVE GUIDANCE AND COLLECTION OF PREGNANCY INFORMATION

### Definitions:

#### Woman of Childbearing Potential (WCBP)

A woman is considered fertile following menarche and until becoming post-menopausal unless permanently sterile (see below)

Women in the following categories are not considered WCBP:

1. Premenarchal
2. Premenopausal female with 1 of the following:
  - Documented hysterectomy
  - Documented bilateral salpingectomy
  - Documented bilateral oophorectomy
3. Postmenopausal female
  - A postmenopausal state is defined as no menses for 12 months without an alternative medical cause. A high follicle stimulating hormone (FSH) level in the postmenopausal range may be used to confirm a postmenopausal state in women not using hormonal contraception or hormonal replacement therapy (HRT). However, in the absence of 12 months of amenorrhea, a single FSH measurement is insufficient.
  - Females on HRT and whose menopausal status is in doubt will be required to use 1 of the non-estrogen hormonal highly effective contraception methods if they wish to continue their HRT during the study. Otherwise, they must discontinue HRT to allow confirmation of postmenopausal status before study enrollment.

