**Female patients**

Female patients of childbearing potential are eligible to participate if they agree to use a highly effective method of contraception throughout the study and for 90 days after the end of study treatment.

Highly effective methods include:

- Combined (estrogen and progestogen containing) hormonal contraception associated with inhibition of ovulation
  - Oral
  - Intravaginal
  - Transdermal
- Progestogen only hormonal contraception associated with inhibition of ovulation
  - Oral
  - Injectable
  - Implantable
- Intrauterine device (IUD)
- Intrauterine hormone-releasing system (IUS)
- Bilateral tubal occlusion
- Vasectomized partner
- Sexual abstinence

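### Inclusion 11 and Appendix 6 set different contraception rules for women, no text says which governs, and inclusion 11 states no requirement during dosing

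*Protocol*

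**What the plan says.** Two parts of the protocol set a contraception condition for entry of women of childbearing potential (WCBP) to the RGI-2001 group.

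- **Inclusion 11**, worded identically in Section 2 and Section 7.1: the woman "must have agreed to use a double barrier method of contraception for 90 days following the last dose of RGI-2001".
- **Appendix 6, Female patients**: "Female patients of childbearing potential are eligible to participate if they agree to use a highly effective method of contraception throughout the study". The full period is "throughout the study and for 90 days after the end of study treatment". The methods listed are combined hormonal, progestogen-only hormonal, intrauterine device (IUD), intrauterine hormone-releasing system, bilateral tubal occlusion, vasectomized partner and abstinence.

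Section 10.7 sends the reader to Appendix 6 "for complete information regarding pregnancies including highly effective contraceptive methods". It does not mention inclusion 11.

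**The concern.** Both texts are worded as conditions of eligibility, yet they name different methods and different periods. A site that screens from Section 7.1 alone would look for an agreement to double barrier. A site that screens from Appendix 6 alone would look for a method on a list that contains no barrier method. The two could decide differently on the same woman, and either decision could later be queried as an eligibility deviation. SAP Section 5.2 lists all deviations and tabulates the major ones.

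The period matters more for safety. Inclusion 11 names only the 90 days after the last dose, so a site relying on Section 7.1 finds nothing that asks women to use contraception while RGI-2001 is being given. Inclusion 12, for men, starts at informed consent.

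**Working it through.** There is no planned figure to reproduce. The check is a comparison of texts.

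| Item | Inclusion 11 (Sections 2, 7.1) | Appendix 6, Female patients |
|---|---|---|
| Method | Double barrier | Highly effective; 7 groups listed |
| Barrier methods named | The one required | 0 of 7 |
| During dosing | Not stated | Covered |
| After the last dose | 90 days | 90 days, plus any longer study period |
| Points to the other text | No | No |

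**Applying each text on its own**

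1. A woman who offers only an IUD meets Appendix 6. She has not given the agreement that inclusion 11 asks for.
2. A woman who offers only double barrier meets inclusion 11. Her method is not on the Appendix 6 list. The only barrier method named in Appendix 6 is the male condom, in the part for male patients, where it is paired with a highly effective method used by the partner.
3. Tubal occlusion does not take a woman outside the rule. Under "Women in the following categories are not considered WCBP", the premenopausal exemptions are hysterectomy, bilateral salpingectomy and bilateral oophorectomy.
4. Women on hormone replacement whose menopausal status is uncertain "will be required to use 1 of the non-estrogen hormonal highly effective contraception methods" if they wish to continue it. Such a method alone does not supply the inclusion 11 agreement.
5. A woman who uses a listed method and also agrees to double barrier meets both texts.

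**Looking for a rule of precedence.** Inclusion 11 does not cite Appendix 6. Section 10.7 cites Appendix 6 but deals with pregnancy reporting and does not alter the criterion. Section 9 requires sites to confirm every eligibility criterion, so inclusion 11 cannot simply be treated as superseded.

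**Period.** Section 6.7 says "Individual subject participation is expected to last up to one year following alloHSCT". Read literally, the Appendix 6 period runs to the end of that year. But with the last dose on schedule at Day 35, the 90-day clause ends at 35 + 90 = Day 125, well inside the year, so on that reading the clause adds nothing. The other reading is treatment plus 90 days, which ends on the same day as inclusion 11. The text does not settle which is meant.

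**Other safeguards during exposure.** The Section 3 schedule marks the serum pregnancy test at screening and at unscheduled visits only, with the screening test within 7 days before the preparatory regimen. No repeat is scheduled across the six weekly doses. Agreed contraception is therefore the main planned protection in that interval, and for women only Appendix 6 states it.

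**The case against.** The strongest reply is that the two texts are compatible. Inclusion 11 tests an agreement about the future, not the woman's current method, and neither text excludes adding a second method. A woman with an IUD can qualify by also agreeing to use barriers. This stands: no exclusion is forced, and following both texts gives more contraception, not less. But nothing says both apply, and Appendix 6 words its own condition as enough for eligibility.

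The list can also be read as non-exhaustive, since it is introduced as what such methods include. That may help a double-barrier user, although no text calls double barrier highly effective. It does nothing for the IUD user under inclusion 11. Section 10.7 does mark Appendix 6 as the fuller source, which hints at the sponsor's intention without settling the matter.

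Three stronger readings are tempting and not supported:

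- *That women are left without a contraception requirement during dosing.* Appendix 6 supplies one. The gap is in inclusion 11 alone.
- *That the two contraception periods differ by many months.* This depends on one reading of the Appendix 6 period; on the other reading the end dates coincide.
- *That the pregnancy reporting rule conflicts with the 90 days.* Section 10.7 covers "Any pregnancies that occur within 150 days for females or 90 days for males following the last dose of study treatment". A reporting window longer than the contraception period is not a contradiction.

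Finally, SAP Section 2.4 describes enrollment in the past tense. If enrollment has closed, the practical benefit of an amendment is small.

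**Conclusion.** The inconsistency is real: two operative eligibility texts name different methods, no rule of precedence connects them, and the criterion sites screen on omits the dosing period for women. It is a minor harmonisation of safety and eligibility wording, worth doing because it is cheap.

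Its reach is limited to women of childbearing potential in the RGI-2001 group. The documents do not say how many there are or which methods they use, so no count of affected women is offered. Pregnancy is an exclusion, and a negative test is required before study drug. Endpoints, selection of controls and analysis are not affected.

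The conclusion assumes that double barrier, which the available text does not define, means two barrier methods used together. It also assumes that the consent form, which was not available, does not already resolve the point.

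**What to change.** 1. Reword inclusion 11 in Sections 2 and 7.1 to require a highly effective method as listed in Appendix 6, during RGI-2001 treatment and for at least 90 days after the last dose.
2. Ask the sponsor to confirm the intended end of the Appendix 6 period, then use the same period wording in both places. Until then, the Appendix 6 period should not be shortened.
3. If the sponsor also wants the requirement to start at informed consent, as inclusion 12 does for men, state openly that this is new for women. Neither current text for women contains it.
4. If double barrier is to remain acceptable, add it to the Appendix 6 list so that one list governs.

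The cost is a wording amendment and a check of the consent form, with no added visits or tests. The downside is that a woman relying on double barrier alone would no longer qualify unless item 4 is adopted.

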## 7.2 Exclusion Criteria

Any subjects (including CIBMTR control group) who meet any of the following criteria will be excluded from study entry:

1. Has had any other prior organ transplantation
2. Planned procedure to deplete regulatory T-cells from donor transplant materials
3. Planned reduced intensity conditioning
4. Planned use of any additional or alternative drug(s) for GvHD prophylaxis than listed in the inclusion criteria (e.g., rapamycin, cyclophosphamide, steroids)
5. Has had prior treatment with anti-CD3, other T cell depleting antibodies, or anti-thymocyte globulin within 12 months prior to alloHSCT procedure
6. Is participating in a trial (other than RGI-2001-003) involving an investigational agent/non-standard of care drug.
7. Has progressive underlying malignant disease including post-transplant lymphoproliferative disease.
8. Has evidence of active central nervous system (CNS) disease including known brain or leptomeningeal disease (CT or MRI scan of the brain required only in case of clinical suspicion of CNS involvement).
9. Known history of human immunodeficiency virus (HIV)
10. Active infection with hepatitis C virus (HCV) or hepatitis B virus (HBV) (control group only)

11. Is female and pregnant or lactating
12. Patients with active bacterial, viral or fungal infections (currently taking medication(s) and with progression or no clinical improvement)

Exclusion criteria pertaining specifically for subjects scheduled to receive RGI-2001:

13. Has undergone major surgery within 1 month before Day 0. Indwelling catheter placement is allowed
14. Hepatitis B virus (HBV) or hepatitis C virus (HCV) infection with viral load above the limit of quantification. Subjects that are on study with HBV or HCV infection should have titers checked regularly, as per institutional standard of care.
15. Has had any other condition that, in the opinion of the Investigator, renders the subject unsuitable for study participation
16. Has a documented history of uncontrolled autoimmune disease or on active treatment
17. Vaccinated with live, attenuated vaccines within 4 weeks of first dose of study drug.
18. History of myocardial infarction, unstable angina, or acute coronary syndrome within 6 months prior to receiving study drug
19. Has received an investigational agent within 4 half-lives or 14 days prior to HSCT, whichever is shorter

### **7.3 Eligibility for the Control Arm**

Subjects in the control arm will be identified from subjects reported to the CIBMTR from U.S. centers and which agree to participate in this study. Control subjects must satisfy the inclusion and exclusion criteria of this study according to [Section 7](#).

Data for all eligible subjects in centers agreeing to participate in the study will be used to constitute the control database for this study.

### **7.4 Donor Screening**

Stem cell or bone marrow donors will be evaluated according to institutional protocol. A bone marrow transplant physician and/or nurse practitioner will perform a complete medical history and physical exam, donor health history questionnaire and Zika virus screening. Required testing will include hematology studies, evaluation of risk for hemoglobinopathy as clinically indicated, chemistry studies, infectious disease testing, EKG, and chest x-ray. Bone marrow donors will also require evaluation and clearance by an anesthesiologist as per institutional practices.

Donors will be considered eligible if screening shows that the donor is free from risk factors for, and clinical evidence of, infection due to relevant communicable disease agents and diseases, and is free from communicable disease risks associated with transplantation (test results for relevant communicable disease agents are negative or nonreactive).

## 7.5 Withdrawal/Discontinuation from Treatment, Procedures and Study

### 7.5.1 *Study Discontinuation*

The Sponsor has the right to terminate this study at any time. Reasons for terminating the study overall or at a specific study site may include, but are not limited to the following:

1. The incidence or severity of adverse events (AEs) in this or other RGI-2001 studies indicates a potential health hazard to subjects
2. Subject enrollment is unsatisfactory
3. Data recording is inaccurate or incomplete
4. Investigator does not adhere to the protocol or applicable regulatory guidelines in conducting the study
5. The safety review committee (SRC) recommends termination of the study due to revealed safety concerns.

### 7.5.2 *Subjects' Decision to Withdraw*

Subjects have the right to withdraw from the study at any time and for any reason without prejudice to their future medical care by the physician or at the institution.

Subjects can decline to continue receiving investigational product and/or other protocol-required therapies or procedures at any time during the study but continue participation in the study. If this occurs, the investigator is to discuss with the subject the appropriate process for discontinuation from investigational product or other protocol-required therapies and must discuss with the subject the options for continuation of the Schedule of Assessments and collection of data, including endpoints and adverse events. The investigator must document the level of follow-up that is agreed to by the subject (e.g., in person, by telephone/mail, through family/friends, in correspondence/communication with other physicians, from review of the medical records).

Withdrawal of consent from a study means that the subject does not wish to receive further protocol-required therapies or procedures, and the subject does not wish to or is unable to continue further study participation. Subject data up to withdrawal of consent will be included in the analysis of the study, and where permitted, publicly available data can be included after withdrawal of consent. The investigator is to discuss with the subject appropriate procedures for withdrawal from the study.

If a subject fails to return for scheduled visits, a documented effort must be made to determine the reason. If the subject cannot be reached by telephone after two attempts, a certified letter should be sent to the subject (or the subject's legally authorized representative, if appropriate) requesting contact with the Investigator. Attempts to contact the subject should be documented in the study records.

### 7.5.3 *Discontinuation of Study Treatment and/or Withdrawal of Subjects Prior to Study Completion*

The investigator and/or Sponsor can decide to withdraw a subject(s) from investigational product and/or other protocol-required therapies, protocol procedures, or the study as a whole at any time prior to study completion. Reasons for removal from protocol-required investigational product or procedural assessments include any of the following:

1. Subject withdrawal of consent
2. Safety concern (e.g., due to an adverse event including those defined as DLT criteria, ineligibility determined, significant protocol deviation, noncompliance, requirement for alternative therapy, pregnancy)
3. Death
4. Lost to follow-up

If a subject develops acute GvHD prior to completing all six RGI-2001 doses, the subject is still permitted to receive any remaining RGI-2001 doses with written approval by the Medical Monitor and if no experimental GvHD treatment is planned.

Subjects who permanently discontinue RGI-2001 prior to receiving all six doses should be encouraged to remain in the study and follow the SOA (see [Section 3](#)) for all remaining study visits primarily for assessment of secondary endpoints.

Subjects who are permanently discontinued from the study, either during the treatment period or follow up period, should complete the Early Termination Visit as per the SOA ([Section 3](#)) and, if applicable, monitor adverse event through 30 days of last RGI-2001 dose.

### 7.6 **Replacement of Subjects**

Subjects in the Safety Run-in Phase who do not complete the DLT window for reasons other than toxicity may be replaced. Similarly, if a subject in the Safety Run-in Phase receives  $\leq 50\%$  of planned doses of RGI-2001 for reasons other than toxicity considered related to RGI-2001, this subject may be replaced. All subjects who receive at least one dose of RGI-2001 in the Expansion Phase will be considered evaluable.

Subjects who have cancelled alloHSCT will also be replaced.

## 8 STUDY DRUG

Refer also to the current sponsor approved study Pharmacy Manual for details.

### 8.1 Physical Description

### 8.2 Packaging and Labeling

RGI-2001 for Injection is supplied as a sterile liquid suspension filled into depyrogenated USP Type 1 5-mL glass vials with a 2.5 mL fill volume, using a closure system consisting of sterilized rubber stoppers (22 mm) with aluminum royal blue seals and flip-off caps. The dosing is based on the dose of the liposome-encapsulated ingredient, RGI7000. Each vial contains 5 mg/mL of RGI7000 and 50 mg/mL of lipid blend in a 10% sucrose solution containing 20 mM Histidine.

The product is for single-use only and does not contain a preservative.

### 8.3 Storage

RGI-2001 should be stored at 2°–8°C, protected from freezing and exposure to light.

### 8.4 Study Drug Accountability

The PI or designee is responsible for maintaining accurate records (including dates and quantities) of IP received, subjects to whom IP is dispensed (subject-by-subject dose specific accounting), and IP lost or accidentally or deliberately destroyed. The PI or designee must retain all unused or expired study supplies until a Sponsor-designated Clinical Research Associate (CRA) has confirmed the accountability data.

### 8.5 Return and Disposition of Study Drug

Unused study drug must be kept in a secure location for accountability and reconciliation by the Sponsor-designated CRA. The Investigator or designee must provide an explanation for any destroyed or missing study drug or study materials.

Unused study drug may be destroyed on site, per the site's standard operating procedures, but only after Sponsor or its designee has granted approval for drug destruction. The Sponsor-designated CRA must account for all study drug in a formal reconciliation process prior to study drug destruction. All onsite study drug destruction must be documented. Documentation must be provided to the Sponsor or its designee and the original retained in the PI's study files. If a site is unable to destroy study drug appropriately, the site can return unused study drug to Sponsor's designee upon request.

All study drug and related materials should be stored, inventoried, reconciled, and destroyed or returned, according to applicable state and federal regulations and study procedures.

## 8.6 Administration and Dosing Regimen

All subjects will receive 6 weekly doses of RGI-2001 100 µg/kg via IV administration over 30 minutes. Weight should be taken within one day of dosing and the dosage of RGI-2001 should be verified to be the same as the planned dose. The dosage of RGI-2001 will be diluted in 50 ml 0.9% normal saline and the first dose will administered intravenously at approximately 30 minutes and no later than 1 hour after completion of the allogeneic HSCT on Day 0 (study Day 1 if transplant occurs over 2 days). If cytokine release/infusion reaction is observed during or after HSCT, then RGI-2001 should be postponed until at least 30 minutes after the reaction has resolved. Subsequent RGI-2001 administrations should be administered on Days 7, 14, 21, 28, and 35 +/- 1 day. Pre-medications should not be administered prophylactically. However, if a grade 2 cytokine release is observed, pre-medication with an antihistamine (e.g., diphenhydramine), an anti-pyretic (e.g. acetaminophen) and corticosteroids (e.g., 4 mg dexamethasone or equivalent) should be administered. Consideration may be made to administer premedication for Grade 1 cytokine release, depending on the constellation of symptoms. In addition, the SRC may recommend pre-medications in all current and future subjects depending on safety reviews.

